1 BACKGROUND AND RATIONALE

1.1 Introduction

Coronary artery calcium scoring allows for the non-invasive evaluation of calcium deposition in the plaques in coronary arteries. Studies have shown direct relationships between CAC scores and histologic, intracoronary ultrasonic, and angiographic measures of plaque burden [1]. Use of CACS has been proposed as an alternative to more expensive and invasive exams, such as coronary computed tomography angiography (CTA) to evaluate the coronary arteries. Thus, the CACS has the potential to be a powerful clinical tool in the workup of cardiac disease.

While CT CACS is an effective and informative diagnostic imaging technique there are several downsides. CT is expensive, it subjects the patient to large amounts of radiation, can be time consuming, and is possibly unavailable if the patient is too large or is unstable. An alternate approach is needed to evaluate CHD and coronary calcium.

Chest tomosynthesis is a reasonable alternative to CT for CAC scoring. Imaging of porcine hearts with artificial CAC has yielded promising results (Image 1). Gated respiratory studies on pigs performed by our lab, (1), demonstrate the gating capabilities of our system. Chest scans of pediatric CF patients, (2), have allowed for accurate Brasfield scoring. Tomosynthesis scans have the advantage of improving upon the currently accepted imaging modality, CT, while simultaneously exposing the patient to 10% the dose of radiation, at 17% the price [4]. The benefits of tomosynthesis suggest that it may be the superior imaging modality for CAC scoring as compared to CT.

Tomosynthesis has already been validated as an imaging technique for breast cancer screening. It has been shown to improve cancer detection rates, decrease false positives, and decrease recall rates [2]. It also has a role in pulmonary nodule detection. Studies have demonstrated an improved detection rate of pulmonary nodules when compared to chest radiography, up to 3 times as many nodules were detected [3, 4].

The proposed research, if successfully implemented, will contribute to the development of a new method for evaluating coronary artery calcium scores (CACS) in individuals with coronary artery disease. Using the Cardiac Gated Stationary Chest Tomosynthesis (CG-SDCT) system the imaging dose for a full tomosynthesis scan is expected to be only 10% of that from a cardiac CT. The targeted imaging time of 25-30 seconds is 1/2 of that from a current commercial DCT system at the same imaging dose. As with current commercial DCT systems, our s-DCT system will expose patients to less radiation and deliver data for CACS that is comparable to CT. CG-SDCT will likely contribute to the development of accurate CAC scoring and allow for a more complete patient risk assessment as compared to Framingham risk scoring alone.

1.2 Hypothesis and Specific Aims

We hypothesize that cardiac gated stationary chest tomosynthesis (CG-SDCT) will be an effective imaging modality for calcium scoring as compared to CT. This method will be more cost effective and expose the patient to far less radiation. We predict that tomosynthesis calcium scoring will result in accurate scoring and allow for a more complete patient risk assessment as compared to Framingham risk scoring alone.

The purpose of this project is to design and implement a novel study that will provide data on the accuracy of calcium scoring by tomosynthesis. If successful, this information can be used to promote larger studies or perhaps warrant the usage of tomosynthesis as the standard imaging modality for calcium scoring.

Aim 1: Perform the first in human cardiac gated stationary chest tomosynthesis.

Aim 2: Perform a reader study and compare Coronary artery calcium scores (CACS) derived from CG-SDCT against conventional CACS.

1.3 Name and Description of Investigational Product or Intervention

The stationary digital chest tomosynthesis (s-DCT) system is based on the carbon nanotube (CNT) x-ray source array technology invented by our team at the University of North Carolina. Instead of mechanically moving a large x-generator to different viewing angles for the projection images, s-DCT generates the images by electronically and sequentially

activating the individual x-ray sources inside spatially distributed CNT x-ray source array without moving the source, detector or the patient.

The clinical test ready prototype device will be constructed by combining the commercial digital radiography system detector (Paxscan 4030) with a dedicated CNT x-ray source array (XinRay Systems Inc., NC). An external collimator is connected to the source array to confine the x-ray radiation only to the region of interests to minimize the radiation to the patient and the staff. A computer station (RealTime Tomography, LLC, PA) will be used for near real-time reconstruction and display of the images.

1.4 Non-Clinical and Clinical Study Findings

The research images will not be interpreted or analyzed for clinical decisions related to the patient. As such, this study will request that the IRB make a determination that this study is no greater than minimal risk. This study meets all the requirements for an NSR determination including:

- The device will not be implanted.
- The device is not intended to support or sustain human life.
- The device is not being used of substantial importance in diagnosing, curing, mitigating, or treating disease.
- The device does not present a potential for serious risk to health, safety, or welfare of a subject

1.4.1 Potential Benefit

There are no anticipated benefits to the study subjects. However, if successfully implemented, the proposed research will result in a low dose, low cost, and highly effective method for evaluating the CACS.

1.4.2 Potential Risks

There is a theoretical risk of loss of confidentiality. The consent, interviews and imaging will be performed in private rooms, and all data will be stored securely to minimize these risks. As with standard chest CT, there is a potential for incidental findings. No incidental findings will be shared as they would be based on experimental, non-FDA approved testing.

Study subjects will be exposed to radiation during participation in this study.

For patients who underwent a clinical chest CT: The s-DCT scan exposes the body to radiation. The estimated additional radiation dose is 30.5 mrem. For comparison, the average person in the United States receives a radiation exposure of 300 mrem per year from natural background source. The additional radiation dose that patients will receive in this study is equal to the radiation everyone receives in 37 days from natural background radiation.

For individuals that will receive a modified CT for TAVR: Additional chest tomosynthesis scan (s-DCT) and CT scan expose the body to radiation. The estimated additional radiation dose is from s-DCT scan is 30.5 mrem. The clinical pre-procedural CT for transcatheter aortic valve replacement (TAVR) will be slightly altered in order to expand the field of view by 6 centimeters. This expanded view exposes patients to slightly higher radiation. The effective radiation dose that patients will receive from added length of the scan 55.5 mrem which is only 2% more than what he/she will receive from the scan without added length. For comparison, the average person in the United States receives a radiation exposure of 300 mrem per year from natural background source. The additional radiation dose from both scans is equal to the radiation everyone receives in 105 days from natural background radiation.

There are unknown risks to a fetus. Pregnancy testing will be performed to exclude pregnancy in women of childbearing potential.

2 STUDY OBJECTIVE

2.1 Primary Objective

The primary objective of the study is to compare CACS between conventionally acquired non-contrast CT and Gated Stationary Chest Tomosynthesis.

2.2 Secondary Objectives

The secondary objectives of this study are:

- To evaluate the practicality of using CG-SDCT in terms of image quality and artifacts.
- To determine the accuracy of gating, which is measured by the correlation of the between the x-ray pulses and the EKG R-wave within a 30ms window around the x-ray pulse.

3 INVESTIGATIONAL PLAN

3.1 Study Design

This is a one arm study of 20 patients who have undergone a clinical, outpatient non-contrast CT at UNC Hospitals for any pathological condition of the chest who consent to undergo an experimental s-DCT.

The study scan, s-DCT, will be performed within four weeks of his/her clinical evaluations by chest CT or a TAVR CT. There cannot be any intervening therapies or procedures (i.e. line placement, biopsy or excision of lesions) done in between the CT chest imaging and the s-DCT.

For patients that receive a CT for transcatheter aortic valve replacement (TAVR), this will require an expansion of the field of view from 5cm to 15cm coverage. This group of patients will receive an additional dose of approximately 30 mSv and these patients must be consented to participate prior to receiving their clinical CT.

Images will be acquired by a trained radiology technologist. The scan will consist of the following procedure. First, the patients, will be asked to change into a hospital gown. The technologist will comfortably position the patient in the supine position on the imaging table. EKG leads will be placed in appropriate positions to derive an EKG signal. Once the EKG signal is verified, the R wave will be selected for triggering the x-ray source. The subject will be asked to hold their breath, then the gated scan will be performed in an anterior-posterior direction. We anticipate that a breath hold of approximately 25 to 30 seconds will be required for the subject, with a single image acquired during each R wave. Images will be reconstructed off-line and transferred for review on conventional PACS workstations. Total patient preparation and imaging time should not exceed 20 minutes.

A reader study will be performed after all patients have been accrued. Each of the scans will be de-identified. As reading of all tests will take place after the patient has undergone clinical decision-making (treatment versus following), the results of this study will not affect patient care. Clinical calcium scoring will be performed using conventional software by trained personnel. Calcific lesions in the distribution of the coronary arteries will be identified on tomosynthesis images and a total score also derived. Readers will be blinded to the calcium score from the other modality. Reader confidence in image quality will also be assessed on a 1 to 10 scale.

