3.2.1 Inclusion Criteria

Subject must meet all of the inclusion criteria to participate in this study.

- (1) Age range: 18 years of age or older
- (2) Intermediate Framingham Risk Score of 10 to 20% risk over the next 10 years
- (3) Previous non-contrast enhanced chest CT in a time frame that will accommodate experimental imaging (CG-SDCT) within 4 weeks. This imaging may have already been completed at the time of enrollment or may be scheduled in the future at the time of enrollment. Alternatively, patients scheduled to undergo a clinical preprocedural CT for transcatheter aortic valve replacement (TAVR) may be included if he/she consents to an expanded field of view in his/her clinical scan.
- (4) IRB written informed consent obtained and signed
- (5) Negative urine pregnancy test in women of child-bearing potential (WCBP) within 1 week prior to s-DCT.

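### TAVR patients' added radiation dose is about 30 mSv in section 3.1 but sums to 0.86 mSv in section 1.4.2, a 35-fold conflict, and the field of view grows by 10 cm in one section and 6 cm in the other

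*Combined protocol and SAP*

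**What the plan says.** Two sections describe the extra radiation for patients recruited through the TAVR CT.

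- **Section 3.1 (Study Design).** On the field of view: "this will require an expansion of the field of view from 5cm to 15cm coverage". The next sentence gives the dose: "This group of patients will receive an additional dose of approximately 30 mSv".
- **Section 1.4.2 (Potential Risks).** The clinical CT "will be slightly altered in order to expand the field of view by 6 centimeters". On the CT extension: "The effective radiation dose that patients will receive from added length of the scan 55.5 mrem". That increment is then compared with the unextended CT: "which is only 2% more than what he/she will receive from the scan without added length". On tomosynthesis: "The estimated additional radiation dose is from s-DCT scan is 30.5 mrem". On the two together: "The additional radiation dose from both scans is equal to the radiation everyone receives in 105 days from natural background radiation". The background rate used is 300 mrem per year.

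Section 3.2.1 makes the wider scan a condition of entry by this route: these patients "may be included if he/she consents to an expanded field of view in his/her clinical scan". Sections 3.1, 4.1 and 9 require their consent before the clinical CT. No section reconciles the two doses or the two lengths.

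**The concern.** The same patients are assigned two additional doses that differ by more than an order of magnitude, in different units, and two different field-of-view expansions.

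Radiation is the main physical risk the protocol describes, and the CT extension is made for research. Section 1.4 asks the IRB to find the study no more than minimal risk. That judgement needs one dose, and here it could rest on about 105 days of background or on about 10 years. The length is also a scanning instruction: staff working from 3.1 would add 4 cm more than 1.4.2 describes (10 − 6), and the risk figures in 1.4.2 are tied to 6 cm.

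The consent form is not in the copy reviewed, so nothing is claimed here about what patients were told.

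**Working it through.** **Inputs.** From 1.4.2: tomosynthesis 30.5 mrem; CT extension 55.5 mrem, stated as 2% of the unextended scan; background 300 mrem per year; extension 6 cm. From 3.1: additional dose about 30 mSv; coverage 5 cm to 15 cm. Conversion: 1 mSv = 100 mrem.

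**1. Reproduce the day counts in 1.4.2** (days = dose / 300 × 365).
- Tomosynthesis alone: 30.5 / 300 × 365 = 37.1 days (stated: 37).
- Both components: 30.5 + 55.5 = 86 mrem = 0.86 mSv; 86 / 300 × 365 = 104.6 days (stated: 105).

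The 86 mrem total is not printed, but the 105 days confirm that it is the intended sum.

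**2. Compare with 3.1.**
- 30 mSv = 3000 mrem; 3000 / 86 = 34.9.
- If 3.1 means the CT extension alone: 30 / 0.555 = 54.
- In background terms: 3000 / 300 = 10 years.

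**3. Is 30 mSv plausible as an increment?** The 2% statement implies an unextended clinical CT of 55.5 / 0.02 = 2775 mrem = 27.75 mSv. The range below allows for 2% having been rounded.

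| True percentage | Implied clinical CT (mrem) | 3000 mrem as a share of it | Clinical CT + 86 mrem |
|---|---|---|---|
| 1.5% | 3700 | 81% | 3786 mrem (37.9 mSv) |
| 2.0% | 2775 | 108% | 2861 mrem (28.6 mSv) |
| 2.5% | 2220 | 135% | 2306 mrem (23.1 mSv) |

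An extra 30 mSv would therefore be about as large as the whole clinical scan.

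A second check does not use the 55.5 mrem or the 2%. Section 1.1 expects tomosynthesis to deliver 10% of a cardiac CT dose. With 30.5 mrem, that implies a cardiac CT of 30.5 / 0.10 = 305 mrem (about 3 mSv), so 3000 mrem would be about ten such scans (3000 / 305 = 9.8).

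**4. Possible origins of the 30.** It could be the 30.5 mrem tomosynthesis dose with the wrong unit, or the total of about 28.6 mSv written as an increment. The documents do not say which.

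**5. Length.** Section 3.1 adds 15 − 5 = 10 cm; section 1.4.2 adds 6 cm. As an illustration only, assume the extension's dose scales with its own length:
- 55.5 / 6 × 10 = 92.5 mrem for the extension.
- 92.5 + 30.5 = 123 mrem in total, or 1.23 mSv, which is 0.37 mSv more than 0.86.
- 123 / 300 × 365 = 149.7 days.
- 92.5 / 2775 = 3.3% of the clinical CT, instead of 2%.
- 3000 / 123 = 24.4, so at 1.4.2's dose per centimetre the longer extension does not close the gap.

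**The case against.** The conflict itself is not in dispute. The strongest objection is to naming 30 mSv as the likelier error. The 37 and 105 days are the same doses divided by 300, so they show that the sum is right, not that 55.5 mrem is the right dose. The 2% comes from the same sentence as the 55.5 mrem, and the 27.75 mSv scan is back-calculated from that sentence. Taken alone, this judges 3.1 by assuming 1.4.2. The point is fair as far as it goes, but the check through section 1.1 does not use that sentence and also makes 30 mSv implausible. The direction therefore remains a well-supported inference, not a proven fact.

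A second objection is that 3.1's dose and length may belong together. Going from 5 cm to 15 cm triples coverage; if dose followed coverage, a 15 mSv scan would gain 30 mSv. So it cannot be said outright that length does not explain the dose gap. That statement is conditional on 1.4.2's dose per centimetre. Scaling is uncertain in the other direction too: 6 cm adding 2% at a uniform dose would imply a scan of 6 / 0.02 = 300 cm. The 10 cm figures are therefore an illustration and should not be written into the protocol.

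It is also true that no stated calculation is wrong (this is a conflict between sections), that only an alternative entry route is affected, and that if 1.4.2 is right, 3.1 overstates the risk and does not hide it. None of this removes the need for one dose and one length.

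**Conclusion.** The concern holds. Sections 3.1 and 1.4.2 give irreconcilable additional doses for TAVR patients: 3000 against 86 mrem, 35-fold if 3.1 covers both components and 54-fold if it covers only the CT extension. They also give different field-of-view expansions, 10 cm against 6 cm.

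The existence and size of the conflict need only the stated figures and the unit conversion. That 30 mSv is the likelier error is an inference from the 2% figure and from the 10% dose expectation in section 1.1. The effect of a 10 cm extension on dose is unknown without a dosimetry calculation.

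This is a participant-safety correction that should be made. It is confined to the TAVR route and does not affect sample size, endpoint or analysis.

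**What to change.** 1. Establish the added length actually used for TAVR CTs and state it identically in 1.4.2 and 3.1. This comes first, because the 55.5 mrem depends on it.
2. Replace the 30 mSv in 3.1 with the confirmed additional dose, split into CT extension and tomosynthesis. If 6 cm is right and the 1.4.2 doses are confirmed, that is 0.555 + 0.305 = 0.86 mSv (86 mrem). Changing only the unit, to 30 mrem, would leave out the extension.
3. If 10 cm is right, have the dose recalculated and update the 55.5 mrem, 2% and 105-day figures in 1.4.2.
4. Use one unit in both sections, and check that the consent form and IRB submission agree.

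The cost is a dose and length check and a short text amendment to two sections.

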3.2 Study Population

The study population will be twenty (20) patients who have undergone clinical outpatient non-contrast CT of the chest will be asked to have a CG-SDCT within 4 weeks (+/- 1 week) of their clinical CT, with no intervening procedure or therapy (i.e. biopsy, line placement, etc). Alternatively, patients scheduled to undergo a clinical CT for transcatheter aortic valve replacement (TAVR) may also be included with a modified field of view.

3.2.1 Inclusion Criteria

Subject must meet all of the inclusion criteria to participate in this study.

- (1) Age range: 18 years of age or older
- (2) Intermediate Framingham Risk Score of 10 to 20% risk over the next 10 years
- (3) Previous non-contrast enhanced chest CT in a time frame that will accommodate experimental imaging (CG-SDCT) within 4 weeks. This imaging may have already been completed at the time of enrollment or may be scheduled in the future at the time of enrollment. Alternatively, patients scheduled to undergo a clinical preprocedural CT for transcatheter aortic valve replacement (TAVR) may be included if he/she consents to an expanded field of view in his/her clinical scan.
- (4) IRB written informed consent obtained and signed
- (5) Negative urine pregnancy test in women of child-bearing potential (WCBP) within 1 week prior to s-DCT.

3.2.2 Exclusion Criteria

All subjects meeting any of the exclusion criteria at baseline will be excluded from study participation.

- (1) Unable to provide consent
- (2) Pregnant or lactating
- (3) BMI > 33 (Patient who may not fit on a 35 x 35 detector) (Images are not clear on subjects who have a greater than 33 BMI)
- (4) Previous history of MI or thoracic surgery.
- (5) Disability that could interfere with the scanning process, non-ambulatory or unable to hold their breath for up to 30 seconds.
- (6) Planned procedures or therapies in between non-contrast CT scan and study Chest tomosynthesis scan, e.g, line placement in the chest region, biopsy, etc.

4 STUDY PROCEDURES

4.1 Screening/Baseline Visit procedures

The referring physician will apprise the potential patient of the study. If they agree to be contacted, the study team will approach the patient in the treating clinic or contact them by telephone. If the patient is interested in participation, he/she will be consented either then (in their treatment clinic) or when he/she arrives to have his/her s-DCT, but prior to any study procedures. Patients with a modified TAVR CT will be consented prior to this imaging. Review of the consent will take place in the privacy of an exam room. Once the patient has consented, women of child bearing potential (WCBP) will be given a urine pregnancy test in order to ensure that they are not pregnant. If a urine pregnancy test shows a result positive for pregnancy, the patient will be excluded from the study per the exclusion criteria.

4.2 Intervention/Treatment procedures (by visits)

Subjects who meet eligibility criteria and who consent to the study will undergo a Cardiac Gated stationary Chest Tomosynthesis (CG-SDCT) within 4 weeks (+/- 1 week) following their clinical CT.

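### For TAVR patients, 4.2 allows up to five weeks between the research-extended CT and the s-DCT, and a valve procedure scheduled or brought forward in that gap would void the pair

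*Combined protocol and SAP*

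**What the plan says.** **Timing.** Section 4.2 places the s-DCT "within 4 weeks (+/- 1 week) following their clinical CT". Section 3.1 says that it "will be performed within four weeks of his/her clinical evaluations by chest CT or a TAVR CT", without the one-week tolerance and without an order. Section 3.2 has the tolerance but no order. Section 3.2.1, item (3), has no tolerance. None of them gives TAVR patients their own timing.

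**Research exposure at the CT.** Section 1.4.2 states: "The clinical pre-procedural CT for transcatheter aortic valve replacement (TAVR) will be slightly altered in order to expand the field of view by 6 centimeters". It gives the added exposure as "The effective radiation dose that patients will receive from added length of the scan 55.5 mrem". Section 3.1 describes an expansion from 5 cm to 15 cm and says "This group of patients will receive an additional dose of approximately 30 mSv". Section 4.1 adds: "Patients with a modified TAVR CT will be consented prior to this imaging". For patients with a clinical chest CT, 1.4.2 lists only the s-DCT as added exposure.

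**Valid pairs.** Section 3.1: "There cannot be any intervening therapies or procedures" between the CT and the s-DCT. Exclusion (6) in 3.2.2, applied at baseline, covers "Planned procedures or therapies in between non-contrast CT scan and study Chest tomosynthesis scan".

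**Analysis set.** Section 5 expects both scans from everyone eligible and enrolled. No section says what happens to a pair interrupted by a procedure, or whether that patient is replaced.

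**The concern.** For a chest-CT patient the interval between scans carries little ethical weight. The CT was done for clinical reasons, and if something intervenes the s-DCT need not be done.

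A TAVR patient is in a different position. The CT itself carries research exposure, which cannot be undone. The same CT is done to prepare for a valve procedure, which is the kind of event that 3.1 does not allow between the scans. If the procedure is scheduled or brought forward after the CT and falls before the s-DCT, the patient has been exposed for research and contributes no usable comparison. One such case is undesirable whatever the total. Statistically, each case also removes a pair from a study planned around 20.

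**Working it through.** **Step 1. Does the gap exist in the text?** Four statements are needed, and each is present:

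- The TAVR CT is altered for research (1.4.2, 3.1).
- The s-DCT may come later, by up to 4 + 1 = 5 weeks at the outer limit (4.2).
- The TAVR CT is pre-procedural (1.4.2, 3.2.1).
- A procedure between the scans is not allowed (3.1).

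**Step 2. What does exclusion (6) catch?** TAVR patients consent before the CT, so baseline precedes the research exposure. A valve procedure already planned for the interval excludes the patient in time. A date first set, or moved forward, after the CT is not visible at baseline. The gap is limited to that second group.

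**Step 3. How large is the research exposure at the CT?**

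- On 1.4.2: 30.5 + 55.5 = 86.0 mrem in total. Check against its own comparison: 86.0/300 × 365 = 104.6 days, which agrees with the stated 105. The CT share is 55.5/86.0 = 64.5%.
- On 3.1: 30 mSv × 100 = 3,000 mrem, which is 3,000/55.5 = 54 times the 1.4.2 figure for the extension. If it referred to the extension alone, the CT share would be 3,000/(3,000 + 30.5) = 99.0%.
- The lengths differ too: 6 cm in 1.4.2, against 15 − 5 = 10 cm in 3.1.

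The sections contradict each other, so no share of dose can be quoted until they are reconciled.

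**Step 4. The plan's own precision figures** (6.3 and 6.4: n = 20, r = 0.6, alpha 0.05, power 0.83, 95% CI 0.215 to 0.823, minimum n 17).

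- Power by Fisher z with bias term: Φ{[atanh(0.6) + 0.6/(2 × 19)] × √17 − 1.96} = Φ(0.96) = 0.832. Simulation of the two-sided test gives 0.836. The stated 0.83 is reproduced.
- CI: tanh(0.693 ± 1.96/√17) = 0.214 to 0.824, which agrees up to rounding.
- Minimum n for power 0.8: a noncentral t calculation with fixed x gives 17 (power 0.824 at 17, 0.797 at 16), as stated. Two-sided simulation under a bivariate normal model gives 19.

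**Step 5. What would lost pairs do?** Simulated two-sided power at r = 0.6 is 0.836 with 20 pairs, 0.815 with 19, 0.790 with 18, 0.764 with 17 and 0.734 with 16.

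The number of TAVR patients (k) and the share treated before the s-DCT (q) are not in the documents. The values below are assumptions. Expected loss is k × q, and the last column is the binomial chance of losing 4 or more, which would leave fewer than 17 of 20.

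| k | q | Expected lost pairs | Chance of losing 4 or more |
|---|---|---|---|
| 5 | 10% | 0.5 | below 0.001 |
| 5 | 25% | 1.25 | 0.016 |
| 5 | 50% | 2.5 | 0.188 |
| 10 | 10% | 1 | 0.013 |
| 10 | 25% | 2.5 | 0.224 |
| 10 | 50% | 5 | 0.828 |

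The spread shows that the answer depends almost wholly on the assumed inputs.

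**The case against.** The strongest reply is that the plan already protects these patients. The ban in 3.1 directly follows a sentence that names the TAVR CT, so it covers this cohort. Exclusion (6) acts before any research exposure. Same-day scanning is already permitted, and five weeks is an outer limit, not the intended interval. The word *following* appears only in 4.2. The sample size is at least 20, so lost pairs could be replaced. All of this stands, and it narrows the point to procedures set or moved after the CT. It does not close the gap: same-day scanning is allowed but not required, and replacing a pair does not undo the first patient's exposure.

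A reader might infer more than the documents support:

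- *That exclusion (6) misses TAVR patients because it speaks of a non-contrast CT.* Sections 2.1 and 4.3 use that term for the study's CT in general. The wording should be tidied, but the intent is clear enough.
- *That valve replacement falls outside the ban because 3.1 does not list it.* The examples there are not a complete list; exclusion (6) ends its own list openly.
- *That about 65% of the added dose precedes the s-DCT.* This holds only on 1.4.2, which 3.1 contradicts.
- *That contrast from the TAVR CT could affect an early s-DCT.* No section says that this CT uses contrast.
- *That the loss is selective and biases the comparison.* The comparison is within patient, and nothing in the documents links time to valve procedure with the difference between the two scores.

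**Conclusion.** The point holds in a limited form. For TAVR patients the plan permits research exposure at the CT and then an interval of up to five weeks, in which a newly scheduled or advanced valve procedure would void the pair. Some patients may therefore be exposed for research without giving usable data.

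The size cannot be computed from the documents. On the plan's own minimum of 17, up to three lost pairs are tolerable, although simulated two-sided power would then be 0.764 rather than 0.836. The main reason to act is the avoidable exposure, and the remedy is cheap. This is a worthwhile improvement, not an error in calculation or a flaw that undermines the study.

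The conclusion assumes that a valve replacement counts as an intervening procedure under 3.1, and that some dates are fixed or changed after the CT. The documents do not say how often that happens.

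**What to change.** 1. **Section 4.2:** schedule the research s-DCT for TAVR patients at the same visit as their CT. They already consent before that CT, and 3.1 puts preparation and imaging for the s-DCT at no more than 20 minutes. This closes the interval in which a procedure can intervene. It does not remove the chance that the s-DCT fails for other reasons, such as gating or breath hold.
2. **Exclusion (6):** refer to the clinical chest CT or TAVR CT, so that it matches 3.1.
3. **Sections 1.4.2 and 3.1:** reconcile the added exposure (55.5 mrem against about 30 mSv) and the added length (6 cm against 5 to 15 cm). Quote no share of dose until that is done.
4. **Section 5 or 6.3:** add one sentence on how an interrupted pair is handled and whether the patient is replaced.

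The extension of the CT should not be made conditional on a usable s-DCT. Section 3.1 has images reconstructed off-line and 7.3 allows seven days for review, so usability may not be known at the visit. Such a rule would also make the reference scan depend on success of the test under study, and would set a rule for a clinical scan. Nothing here concerns the indication for the clinical CT or the timing of the valve procedure.

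The cost is a short amendment and the effort of fitting the s-DCT to the CT appointment.
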